Objectives	 The objectives of the study are: To characterize the variability in the pharmacologic response to NSAIDs in healthy adults To investigate clinical, genetic, and environmental factors that contribute to this variability To explore the dynamics and variability of the molecular NSAID response network using "omics" data To identify candidate genetic modifiers in the function of the COX pathway at baseline and in response to NSAIDs To establish a well-phenotyped cohort of subjects, with biobanked samples, that can be re-contacted about participation in future studies of NSAID response 								
Number of Subjects	288								
Diagnosis and Main Inclusion Criteria	Adult men and women greater than 18 years of age who are in good health based on medical history, physical examination, vital signs, and laboratory tests. Volunteers with adequately controlled hypertension and hyperlipidemia (total cholesterol of ≤270 mg/dL) may participate in the study.								
Study Product, Dose, Route, Regimen	Celecoxib (Celebrex), 100 or 200 mg orally twice daily Naproxen (Naprosyn), 250 or 500 mg orally twice daily								
Duration of administration	7 days								
Reference therapy	Placebo								
Statistical Methodology	The effect of clinical, genetic, and environmental variables on response to NSAID treatment will be evaluated. Exploratory transcriptomic, proteomic, metabolomic, and microbiome analyses will be performed.								

[contact]

Email: [contact]

[contact]

PERSONNEL

Principal Investigator:

[name].

Address: Department of Pharmacology

Institute for Translational Medicine and Therapeutics

Translational Research Center

[name]

[name]

[name]

Co- Investigators:	Title:	Contact Information:
[name]	Pharm.D., Ph.D.	[name] [contact] e-mail: [contact]
[name]	MD	[name] [contact] e-mail: [contact]
[name]	MD	[name] [contact] e-mail: [contact]
[name]	MD	[name] [contact] e-mail: [contact]

Other Investigators:	Title:	Contact Information:	Responsibilities:
[name]	RN	[name] Hospital of the University of Pennsylvania [name] [contact] [contact] e-mail: [contact]	Clinical Research Coordinator

This protocol is part of the collaborative effort by the Personalized NSAID Therapy Consortium (www.pentaconhq.org), a group of ~35 investigators in 18 institutions, funded by the National Heart Lung and Blood Institute to explore approaches to improve the prediction of risk and benefit of NSAIDs for individuals.

1.1 Background

Non-steroidal anti-inflammatory drugs (NSAIDs) are commonly used for the treatment of inflammatory pain. Pain is a highly subjective experience, and selecting an analgesic regimen that provides optimal pain relief for a specific patient can be challenging. Moreover, patients often express a preference for a particular NSAID, raising the possibility that the efficacy in relieving pain is variable among individuals. However this has never been studied systematically. The clinical decision-making process has been further complicated by the recognition that NSAIDs cause serious thrombotic adverse events in some patients.¹ Elucidating the factors that influence an individual patient's risk of cardiovascular complications and the likelihood of analgesic efficacy will enable clinicians to prescribe NSAIDs rationally in order to maximize their therapeutic benefit while minimizing the risk of adverse cardiovascular events.

NSAIDs are a chemically diverse class of therapeutic agents that exert their analgesic and anti-inflammatory effects via inhibition of cyclooxygenase (COX)-1 and/or COX-2, enzymes that catalyze the first committed step in prostaglandin (PG) synthesis. PGs produce a diverse array of biologic effects via activation of prostanoid receptors, and play important roles in a variety of pathologic and homeostatic processes.² COX-2 is readily induced in response to pro-inflammatory stimuli and has been considered the primary source of inflammatory PGs. In contrast, the production of PGs with homeostatic functions, such as gastric epithelium cytoprotection, has been ascribed to COX-1, which is constitutively expressed in most tissues.² Consequently, COX-2-selective NSAIDs, including rofecoxib, valdecoxib, and celecoxib, were developed in order to retain the anti-inflammatory and analgesic effects of inhibition of COX-2-derived PG formation, while avoiding the gastrointestinal toxicity of traditional NSAIDs (i.e. aspirin, ibuprofen, naproxen, etc) that inhibit both isoforms. Although fewer gastrointestinal complications were observed in clinical trials, treatment with COX-2-selective NSAIDs increased the risk of serious cardiovascular adverse events, including myocardial infarction, stroke, and heart failure.^{1,3}

The risk of thrombotic events associated with the use of NSAIDs, particularly those selective for COX-2, is mediated via suppression of COX-2-derived prostacyclin formation in endothelial and vascular smooth muscle cells.^{4,5} Prostacyclin possesses potent anti-thrombotic and vasodilatory effects, and thus acts as a general inhibitor of platelet activation *in vivo*.² Traditional NSAIDs also inhibit COX-2 in the vasculature, but the associated risk of thrombosis is mitigated to some extent by inhibition of formation of thromboxane A₂ (TxA₂), a COX-1-derived PG released by activated platelets that promotes platelet activation and aggregation.^{1,3} Thus, the risk of thrombosis for a particular NSAID is dependent upon its relative selectivity for COX-2 over COX-1.^{3,6} In addition to their effects on vascular PG production, all NSAIDs inhibit renal PG formation, resulting in sodium retention and hypertension, which may further augment cardiovascular risk.^{1,3,7}

Currently, it is recommended that NSAIDs be avoided or used only for a limited duration in patients classified as high cardiovascular risk.⁸ These recommendations are supported by studies demonstrating that even short-term NSAID use increased the incidence of cardiovascular events in patients undergoing coronary artery bypass grafting^{9,10} and following a myocardial infarction.^{11,12} However, long-term treatment with COX-2-selective NSAIDs also increased the incidence of cardiovascular events in patients considered to be at low baseline risk,^{13,14} consistent with risk transformation due to atherogenesis and indicating traditional cardiovascular risk factors alone are not sufficient to guide therapeutic decisions. Thus, additional studies are necessary to define comprehensively the factors that modify the cardiovascular risk of NSAID use and facilitate the progressive personalization of NSAID therapy.

1.2 Investigational Agent

Celecoxib and naproxen are FDA approved medications for pain and inflammatory diseases. The study drugs will be all administered at FDA approved therapeutic doses.

Celecoxib is a non-steroidal anti-inflammatory drug that selectively inhibits COX-2. It is approved for the treatment of osteoarthritis (100 mg twice daily), rheumatoid arthritis (up to 200 mg twice daily), juvenile rheumatoid arthritis (based on body weight up to 200 mg per day in two doses), ankylosing spondylitis (up to 400 mg per day in one or divided in two doses), acute pain (400 mg initially, followed by an additional 200 mg dose if needed on the first day), gout (800 mg initially followed by 400 mg every 12 hours for 7 days), and primary dysmenorrhea (200 mg twice daily). Celecoxib is contraindicated in patients with known hypersensitivity to celecoxib, aspirin, or other NSAIDs, in patients who have demonstrated allergic-type reactions to sulfonamides, and in patients who have experienced asthma, urticaria, or allergic-type reactions after taking aspirin or other NSAIDs. Severe anaphylactoid reactions to NSAIDs, some of them fatal, have been reported in such patients. Celecoxib is also contraindicated for the treatment of perioperative pain in patients who have recently undergone coronary artery bypass graft (CABG) surgery. Like other NSAIDs, celecoxib carries the risk of gastrointestinal ulceration, bleeding, and perforation. All of the above risks are considered low with a short period (7 days) of administration in subjects who will be thoroughly interviewed as to whether they have allergies to NSAIDs or NSAID-containing medications.

Naproxen is a non-steroidal anti-inflammatory drug that inhibits both COX-1 and COX-2. It is approved for the treatment of osteoarthritis (250-500 mg twice daily), rheumatoid arthritis (250-500 mg twice daily), juvenile rheumatoid arthritis (10 mg/kg/day in two divided doses), ankylosing spondylitis (250-500 mg twice daily), gout (750 mg initially followed by 250 mg every 8 hours), and acute pain, including bursitis, tendinitis, and primary dysmenorrhea (500 mg initially followed by 250 mg every 6-8 hours or 500 mg every 12 hours as needed). Naproxen is contraindicated in patients with known hypersensitivity to naproxen, aspirin, or other NSAIDs and in patients who have experienced asthma, urticaria, or allergic-type reaction following aspirin or other NSAID administration. Severe anaphylactoid reactions to NSAIDs, some of them fatal, have been reported in such patients. Naproxen is also contraindicated for the treatment of perioperative pain in patients who have recently undergone coronary artery bypass graft (CABG) surgery. Like other NSAIDs, naproxen carries the risk of gastrointestinal ulceration, bleeding, and perforation. All of the above risks are considered low with a short period (7 days) of administration in subjects who will be thoroughly interviewed as to whether they have allergies to NSAIDs or NSAID-containing medications.

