3.1 General Design

The study is a double-blind, placebo-controlled trial investigating the pharmacologic response to celecoxib and naproxen in healthy adults. Subjects will be assigned to one of two treatment arms: a low dose arm and a high dose arm. Each treatment phase will be 7 days followed by a 3 day post-treatment assessment and a 2 week wash-out period. The order of the three treatment phases (celecoxib, naproxen, and placebo) will be randomized. The study schema is shown in the figure below:

Qualified subjects will have approximately 9 weeks of participation in this study (1 week/treatment phase x 3 treatment phases + 3 days/post-treatment assessment x 3 post-treatment assessments + 2 weeks/washout phase x 2 washout phases).

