4.2 Exclusion Criteria

- 1. Female subjects who are pregnant or nursing a child.
- 2. Subjects who have received an investigational drug or used an experimental medical device within 30 days prior to screening, or who gave a blood donation of ≥ one pint within 8 weeks prior to screening.
- 3. Subjects with any coagulation, bleeding or blood disorders.
- 4. Subjects who are sensitive or allergic to celecoxib (Celebrex) or naproxen (Naprosyn) or their components.
- 5. Subjects who are sensitive or allergic to aspirin or other NSAIDs.
- 6. Subjects with documented history of any gastrointestinal disorders, including bleeding ulcers.
- History of significant cardiovascular disease (including stroke or TIA), renal, hepatic, respiratory (except infections which longer > 6 months prior to screening), immune, endocrine, hematopoietic disorder or neurological disorders.
- 8. History of cancer within the last 5 years (except for cutaneous basal cell or squamous cell cancer resolved by excision, or carcinoma in situ of the cervix adequately treated).
- 9. Has taken any prescription medication other than hormone replacement therapy (including males taking testosterone as a hormone replacement to treat a documented low testosterone level), thyroid replacement hormones, anti-hyperlipidemic agents, or anti-hypertensive medications. Individuals taking other/additional chronic stable medications can be considered on a case-by-case basis for inclusion in the study if agreed upon by judgment of the investigators.
- 10. Has taken the following NSAID or antisecretory agents within 2 weeks prior to study drug administration:
 - a. Nonsteroidal anti-inflammatory drugs (NSAIDs) including acetaminophen or other medications for pain, including aspirin or aspirin-containing products
 - b. Proton pump inhibitors, including Prilosec®, Prevacid®, Aciphex®, Protonix®, or Nexium® (antacid medications, including OTC products, are not permitted within 24 hours of dosing)
 - c. H₂ blockers, including Tagamet®, Zantac®, Axid®, or Pepcid®
- 11. Has ever taken the following anti-platelet or anti-coagulant agents:
 - a. Any anti-platelet agent, including Aggrenox®, Brilinta®, Plavix®, Ticlid®, Pletal®, ReoPro®, Integrilin®, Aggrastat®, Persantine®, or Effient®
 - b. Any anti-coagulant including Arixtra®, Coumadin®, acenocoumarol, Lovenox®, phenprocoumon, phenindione, heparin, Exanta®, Pradaxa®, argatroban, lepirudin, hirudin, bivalirudin, or Xarelto®

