- 12. Used dietary or herbal supplements containing salicylates, Vitamin E, fish oil, or any other herbal supplements, within 14 days of study drug administration.

- 13. Subjects with any abnormal laboratory value or physical finding that according to the investigator may interfere with interpretation of the study results, be indicative of an underlying disease state, or compromise the safety of a potential subject.
- 14. Subjects who have had a history of drug or alcohol abuse within the last 6 months.
- 15. Subjects who are unwilling to provide a blood sample for genetic analyses and creation of a lymphoblastoid cell line.

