5.7 Packaging

Study drug will be supplied in bulk shipments and blinded by over-encapsulation by the IDS. The IDS will package blinded study medication on-site, as blister packs containing twelve capsules per blister pack. Each blister pack represents the drug supply for at-home drug treatment for a single treatment phase. The last dose, which will be administered on Day 7 in the CTRC, will be packaged separately. Subject

study drug supply will be packaged in kits of 3 blister packs plus the last study medication dose, one for each treatment phase. Each kit will represent the entire drug supply for one study subject.

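### Prior sulfonamide reaction is a stated contraindication to celecoxib, but no eligibility criterion excludes it and every subject is scheduled for celecoxib

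*Combined protocol and SAP*

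**What the plan says.** Section 1.2 (Investigational Agent) lists the contraindications to celecoxib. One is hypersensitivity to celecoxib, aspirin or other NSAIDs. Another is a history of asthma, urticaria or allergic-type reactions after aspirin or NSAIDs. A third is its use for perioperative pain after recent CABG. The list also says the drug is contraindicated "in patients who have demonstrated allergic-type reactions to sulfonamides". The paragraph then calls the risks low for a 7-day course in "subjects who will be thoroughly interviewed as to whether they have allergies to NSAIDs or NSAID-containing medications".

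Two exclusions in section 4.2 concern drug allergy. Exclusion 4 reads "Subjects who are sensitive or allergic to celecoxib (Celebrex) or naproxen (Naprosyn) or their components", and exclusion 5 reads "Subjects who are sensitive or allergic to aspirin or other NSAIDs". Exclusion 13, the discretionary criterion, begins "Subjects with any abnormal laboratory value or physical finding that according to the investigator may interfere with interpretation of the study results".

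On exposure, section 3.1 states: "The order of the three treatment phases (celecoxib, naproxen, and placebo) will be randomized". Section 5.2 includes celecoxib in both dose arms, at 100 mg or 200 mg twice daily.

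**The concern.** The protocol names a group of people who should not receive celecoxib and then does not tell site staff to keep them out. In a parallel-group trial only those allocated to celecoxib would be exposed. Here every subject crosses over through a celecoxib phase, so no arm or sequence avoids the drug. Dosing is double-blind (section 5.8), so staff at the bedside would not know which phase carries it. The subjects are healthy volunteers who take the drug for research, not to treat a condition of their own. The issue is one of subject safety and of consistency between the background section and the eligibility rules.

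**Working it through.** No power or sample size figure is involved. The check compares the contraindications with the criteria and then works out the scheduled exposure.

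**Step 1. Contraindications in section 1.2 against the criteria.**

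| Celecoxib contraindication | Criterion that reaches it |
|---|---|
| Hypersensitivity to celecoxib, aspirin or other NSAIDs | Exclusions 4 and 5 |
| Asthma, urticaria or allergic-type reaction after aspirin or NSAIDs | Exclusion 5 |
| Perioperative pain after recent CABG | Use does not arise in this trial; exclusion 7 (significant cardiovascular disease) reasonably covers the history |
| Allergic-type reaction to sulfonamides | None |

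**Step 2. Count of criteria.** Section 4.1 has 10 and section 4.2 has 15, so 10 + 15 = 25. Criteria that name sulfonamides: 0 of 25. In the available text, sulfonamides are mentioned only in section 1.2.

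**Step 3. Could another criterion apply indirectly?**

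- Exclusion 4 requires allergy to a study drug or its components. Someone who reacted to a different sulfonamide and has never taken celecoxib does not plainly meet it, and section 1.2 lists the two items separately.
- Exclusion 7 includes immune disorders, but it is not a drug-allergy rule.
- Exclusion 13 requires a laboratory value or physical finding. A past drug reaction is neither.
- Inclusion 2 asks for good health judged partly on medical history. It leaves room for judgment but sets no allergy rule.

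**Step 4. The interview offered as mitigation.** The same interview sentence closes the naproxen paragraph of section 1.2. That paragraph begins its contraindications with "Naproxen is contraindicated in patients with known hypersensitivity to naproxen, aspirin, or other NSAIDs", and every allergy it lists relates to NSAIDs, so an NSAID interview covers them all. For celecoxib, the same sentence leaves sulfonamides out.

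**Step 5. Scheduled exposure.**

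- Subjects due to receive celecoxib: 144 low dose + 144 high dose = 288, which is everyone.
- Doses per celecoxib phase: section 5.7 supplies 12 capsules in a blister pack and adds "The last dose, which will be administered on Day 7 in the CTRC, will be packaged separately". So 12 + 1 = 13. The schedule agrees: 2 doses on the first day, 2 × 5 = 10 on the next five days, and 1 on the morning of the seventh, and 2 + 10 + 1 = 13.
- Doses outside the clinic: section 5.9.3 has the first dose taken in the CTRC, and the last is also taken there, so 13 − 2 = 11. Section 5.7 describes the whole 12-capsule pack as the at-home supply. The figure of 11 comes from subtracting the supervised first dose.
- Time in the clinic after the first dose of a phase: arrival is at about 7:30 and dosing at 8:00 (section 6.12.2). The flowchart in section 16.1 allots 1 hour for that visit. So 7:30 + 1 h = 8:30, or about 0.5 hour after dosing. This is inferred: section 5.9.3 requires an observation period but gives no length.

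**The case against.** The strongest reply is that screening may already catch these volunteers. The online questionnaire decides who proceeds to the screening visit (section 4.3), and its screenshots (section 16.11) are not visible in the available text, so a sulfonamide question cannot be ruled out. A complete medical history and a full medication history are also taken, inclusion 2 makes medical history a basis for eligibility, and the investigator may end participation in a subject's interest (section 4.4.1). It is therefore not shown that such a person would in fact be dosed. That stands, and it confines the point to the written criteria. It does not remove the point. A question with no matching criterion gives staff no rule for acting on a positive answer, and the protocol did write explicit rules for study-drug and NSAID allergy where it could have relied on judgment.

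Two smaller points are also fair. Counting CABG as covered is a matter of reading, since no criterion names it. The dose and observation figures show what an admitted subject would face but do not bear on whether the exclusion is missing. The conclusion depends on neither.

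Section 1.4 describes drug allergies among the severe adverse events as rare. That is a general statement, is not specific to people with a prior sulfonamide reaction, and does not override the stated contraindication.

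**Conclusion.** The concern holds. A contraindication stated in section 1.2 has no counterpart among the 25 criteria in sections 4.1 and 4.2, while all 288 planned subjects are scheduled for celecoxib. The number of affected volunteers cannot be estimated, because the documents give no prevalence of sulfonamide reactions. An enrolled subject with this history would be scheduled for 13 celecoxib doses, 11 of them away from the clinic.

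The conclusion rests on the written eligibility rules and assumes nothing about what the questionnaire asks. First-dose observation limits the risk but does not replace an exclusion. The primary endpoints, sample size and analysis are unaffected. Because this is a safety gap that the protocol's own text identifies, it should be corrected, not left to discretion.

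**What to change.** Make three changes by amendment:

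1. Add to section 4.2: *Subjects with a history of allergic-type reactions to sulfonamides.*
2. Extend the interview sentence at the end of the celecoxib paragraph in section 1.2 so that it also covers sulfonamides.
3. Confirm that the screening questionnaire and the medical history ask about sulfonamide reactions, and add the question if they do not.

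The cost is one eligibility line, one revised sentence and at most one screening question. Volunteers with this history become ineligible; the documents do not allow their number to be estimated. The design and the sample size calculation stay as they are.

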1.3 Clinical Data to Date

We have previously demonstrated high inter-individual variability in the pharmacologic response to a single dose of the COX-2 selective NSAIDs celecoxib and rofecoxib, ¹⁵ but the inter-individual variability in response to a traditional and COX-2 selective NSAID at steady state has not been evaluated. The outcome of drug treatment in an individual patient reflects a complex interaction of multiple factors, including demographic and clinical variables, genetic variation, gene and protein expression levels, drug exposure/pharmacokinetics, and environmental exposures. To date, a comprehensive investigation of how these factors influence the pharmacologic response to NSAIDs has not been performed. Preliminary studies in our laboratory suggest that the expression of COX-1 and COX-2 in lymphoblastoid cell lines (LCLs) varies among individuals by greater than 50-fold and greater than 300-fold, respectively. However, it is unknown whether this inter-individual variability in gene expression influences the pharmacologic response to NSAIDs. Moreover, how variation in the genome, transcriptome, proteome, microbiome and metabolome influences the pharmacologic response to traditional and COX-2 selective NSAIDs has not been investigated to date. Such studies may provide insight into the biologic networks that influence the outcome of NSAID therapy and provide the requisite preliminary data to design prospective studies to identify biomarkers to personalize NSAID therapy.

1.4 Dose Rationale and Risk/Benefits

Celecoxib will be administered at a dose of 100 mg (low dose arm) or 200 mg (high dose arm) orally twice daily for 7 days. Naproxen will be administered at a dose of 250 mg (low dose arm) or 500 mg (high dose

arm) orally twice daily for 7 days. These dose regimens are clinically used in the treatment of rheumatoid arthritis, and are being used in the Prospective Randomized Evaluation Of Celecoxib Integrated Safety Vs Ibuprofen Or Naproxen (PRECISION) trial, ¹⁶ which is a prospective trial comparing the cardiovascular safety of celecoxib, naproxen, and ibuprofen. The half-lives of celecoxib and naproxen are 11 hours and 12-15 hours, respectively. Thus, the treatment duration of 7 days was chosen to ensure that drug plasma concentrations have reached steady state.

NSAIDs are generally considered safe drugs for short term treatments, and some NSAIDs are available as over-the-counter (OTC) painkillers in low doses. For example, naproxen is available OTC as a 200 mg dose. Higher does, including the doses used here (250 mg and 500 mg) require a prescription. Celecoxib is a prescription medicine at all doses. All NSAIDs may cause allergic reactions including asthma, urticaria, or allergic-type skin reactions and severe anaphylactic reactions. All NSAIDs can lead to the onset of new hypertension or worsening of preexisting hypertension. All NSAIDs may cause renal adverse events, including fluid retention and edema, and renal toxicity. All NSAIDs may cause gastrointestinal adverse events including heartburn, diarrhea, abdominal distress, nausea and vomiting, indigestion, constipation, abdominal cramps or pain, fullness of GI tract (bloating and flatulence), ulceration and bleeding. Chronic use of NSAIDs may increase the risk of myocardial infarction, stroke and thrombosis, although this has only been shown for celecoxib in randomized trials. Central nervous system adverse effects include dizziness, headache, nervousness, and tinnitus.

Here the treatment duration will be short (7 days) when compared to treatment durations required to relieve symptoms of arthritis or spondylitis. Thus, the risks from study drugs are deemed low, particularly as these are volunteers without prior history of gastrointestinal or renal disease, and without previous serious cardiovascular events such as myocardial infarction, stroke, revascularization procedures and thrombotic events. Severe adverse events of the study drugs such as bleeds, gastrointestinal bleeds, hypertension, renal failure, myocardial infarction and stroke, drug allergies and death are rare.

2 Study Objectives

[figure not shown]
There are several objectives for this study:

- 1. To determine the range of variation of *ex vivo* and *in vivo* markers of COX function at baseline and at steady state concentrations of naproxen and celecoxib in comparison to placebo
- To explore factors that may account for the observed variability in COX function at baseline and following NSAID treatment, including demographic factors, pharmacokinetics, variability in COX pathway gene expression, and the gut microbiome
- To explore the dynamics and variability of the molecular NSAID response network using "omics" data
- 4. To identify candidate genetic modifiers in the function of the COX pathway at baseline and in response to NSAIDs
- 5. To establish a well-phenotyped cohort of subjects, with biobanked samples, that can be recontacted about participation in future studies of NSAID response.

3 Study Design

